## 9.2 SAMPLE SIZE DETERMINATION

A total sample size of 300 subjects (150 subjects per arm) yields approximately 99% power to establish superiority of TP-03 to vehicle in the participants meeting the primary efficacy endpoint assuming a response rate of 80.0% in TP-03 and 15.8% for vehicle treatments, respectively using Pearson chi-squared to test a 1-sided hypothesis with a significance level of 0.025. Response rates for sample size calculations are based upon a prior OUS clinical study of TP-03, 0.25%, for the treatment of *Demodex* blepharitis.

Based on the results of a more recent Phase 2b/3 study, TRS-009 (Saturn-1), with a response rate of 44.0% for the TP-03 treatment group and 7.4% for the vehicle treatment group, a total sample size of 300 subjects still provides greater than 99% power.

The study will be considered a success and TP-03, 0.25%, will be considered superior to vehicle in clinical cure if  $H_0$  is rejected in favor of  $H_1$ . With this sample size, the study will have > 95% power to claim success for clinical cure. A closed hierarchical testing structure will be used such that the analysis will first be performed for the primary efficacy endpoint. [REDACTED]

Accounting for a 30% discontinuation, approximately 209 subjects per arm (approximately 418 total) will be randomized. The planned enrollment is much greater than typically planned to achieve 300

completed subjects due to concerns regarding the impact of COVID-19 and the possibility that up to two sites are unable to complete the study.

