Based on the results from TRS-009 (Saturn-1) with response rates of 67.9% in the TP-03 treatment group and 17.6% in the vehicle treatment group for *Demodex* eradication and 13.9% in the TP-03 treatment group and 1.0% in the vehicle treatment group for composite cure, a sample size of 300 subjects still provides greater than 99% power to demonstrate superiority of TP-03 to vehicle for each endpoint.

For erythema cure, a sample size of 300 subjects will provide 88% power to demonstrate superiority of TP-03 to vehicle at a one-sided significance level of 0.025 based on the results from TRS-009 (Saturn-1), response rate of 19.1% for TP-03 and 7.4% for vehicle.

The study will be considered a success and TP-03, 0.25% will be considered superior to vehicle in clinical cure if H_{01} is rejected in favor of H_{11} . With this sample size, the study will have > 95% power to claim success for clinical cure. A closed hierarchical testing structure will be used such that the analysis will first be performed for the primary efficacy endpoint. Only if the null hypothesis for the primary efficacy endpoint is rejected will analyses be performed for the three secondary efficacy endpoints using the Hochberg testing strategy. Additional details can be found in [Section 8.5](#). If in addition to success for clinical cure, the largest p-value among the secondary endpoints allows for rejection of the null hypothesis in favor of the alternative hypothesis at a significance level of 0.025 then the study will also claim superiority of TP-03, 0.25%, to vehicle for all secondary endpoints. If the study cannot reject the null hypothesis for the secondary endpoint with the largest p-value, the next largest p-value among the remaining two endpoints will be evaluated at a significance level of 0.0125. The study will claim superiority of TP-03, 0.25%, to vehicle for both remaining endpoints if the null hypothesis is rejected in favor of the alternative hypothesis. If the study cannot reject the null hypothesis, the remaining secondary endpoint will be evaluated at a significance level of 0.0083. If the null hypothesis is rejected in favor of the alternative, the study will be able to claim success for the remaining secondary endpoint.

Accounting for a 30% discontinuation, approximately 209 subjects per arm (approximately 418 total) will be randomized. The planned enrollment is much greater than typically planned to achieve 300 completed

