subjects due to concerns regarding the impact of COVID-19 and the possibility that up to two sites may be unable to complete the study.

6. Data Preparation

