13.1 Primary Analysis

The primary efficacy endpoint is cure defined as collarette score of 0 for the upper eyelid of the analysis eye at Day 43. Descriptive statistics will be presented by treatment arm. Testing of the percentage of subjects cured at Day 43 based on the collarette grade will be completed using a difference of proportions test.

The primary efficacy endpoint analysis will be conducted on the FAS, with intercurrent events handled as described in [Section 2.6](#). Discontinuation of study medication and non-optimal compliance will be ignored. Missing data due to withdrawal due to lack of efficacy or AEs will be imputed as failure. Missing data without withdrawal or withdrawal due to reasons other than lack of efficacy or AEs will be imputed employing MI using randomized treatment-based MCMC methodology. The MCMC method simulates missing data under a missing at random assumption while accounting for the uncertainty in the imputed values. Missing values will be imputed with an arbitrary missing pattern. The procedure will use the posterior mode from the EM algorithm as the starting values for the MCMC method. The following SAS® code will be used to generate the multiple imputation datasets:

```
PROC MI DATA=INDATA SEED=19107 NIMPUTE=20 OUT=OUT1 MINIMUM=0 MAXIMUM=4 ROUND=1;
  BY TRT;
  MCMC INITIAL=EM;
  VAR BASE DAY08 DAY15 DAY22 DAY43;
RUN;
```

where

- INDATA is the name of the input dataset
- OUT1 is the name of the output dataset
- TRT is the name of the treatment group variable
- BASE is the baseline assessment
- DAY08 is the assessment at Day 8
- DAY15 is the assessment at Day 15
- DAY22 is the assessment at Day 22
- DAY43 is the assessment at Day 43

The MI datasets will be used to calculate cure based on a collarette score of 0 at Day 43. The following SAS® code will then be used to calculate the difference of proportions for each imputed dataset and combine the analyses across imputations:

```
PROC SORT DATA=OUT1; BY _IMPUTATION_; RUN;
```

where

- OUT1 is the name of the input dataset
- _IMPUTATION_ is the imputation number

and

```
PROC FREQ DATA=OUT1;
  BY _IMPUTATION_;
  TABLES TRT*CURE / RISKDIFF CL;
  ODS OUTPUT RISKDIFFCOL2=PROP;
RUN;
```

where

- OUT1 is the name of the input dataset
- _IMPUTATION_ is the imputation number
- TRT is the name of the treatment group variable
- CURE is the indicator for cure based on a collarette score of 0 at Day 43
- PROP is the name of the output dataset

and

```

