13.1.1.1 SENSITIVITY ANALYSIS I

The primary efficacy analysis will be performed on the FAS set using the difference of proportions test. The hypothetical strategy introduced in [Section 2.6](#) will be used for the intercurrent event, where missing data will be imputed assuming missing not at random (imputing from the vehicle treatment arm). Discontinuation of study medication and non-optimal compliance will be ignored. The following SAS® code will be used to generate the MI datasets:

```
PROC MI DATA=INDATA SEED=43623 NIMPUTE=20 OUT=MDATA MINIMUM=0 MAXIMUM=4 ROUND=1;
  BY TRT;
  MCMC IMPUTE=MONOTONE;
  VAR BASE DAY08 DAY15 DAY22 DAY43;
RUN;
PROC MI DATA=MDATA SEED=346238 NIMPUTE=1 OUT=OUT1 MINIMUM = . 0 0 0 0 0 MAXIMUM
= . 4 4 4 4 4 ROUND = . 1 1 1 1 1;
  BY _IMPUTATION_;
  CLASS TRT;
  MONOTONE REG(DAY08 = BASE/DETAILS);
  MONOTONE REG(DAY15 = BASE DAY08/DETAILS);
  MONOTONE REG(DAY22 = BASE DAY08 DAY15/DETAILS);
  MONOTONE REG(DAY43 = BASE DAY08 DAY15 DAY22/DETAILS);
  MNAR MODEL(BASE DAY08 DAY15 DAY22 DAY43 / MODELOBS=(TRT='Vehicle'));
  VAR BASE DAY08 DAY15 DAY22 DAY43;
RUN;
```

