13.2 Secondary Analyses

The secondary efficacy endpoints are the proportion of subjects with *Demodex* eradication (mite density of 0 mites/lash) at Day 43; the proportion of subjects cured based on a composite collarette and erythema score of 0 at Day 43; and the proportion of subjects cured based on an erythema score of 0 at Day 43. All secondary endpoint analyses will be conducted on the FAS.

As specified in [Section 8.2](#), missing data without withdrawal or withdrawal due to reasons other than lack of efficacy or AEs will be imputed employing MI using randomized treatment-based MCMC methodology.

The following SAS® code will be used to generate the MI datasets:

```
PROC MI DATA=INDATA SEED=10719 NIMPUTE=20 OUT=OUT1 MINIMUM=0 MAXIMUM=4 ROUND=1;
  BY TRT;
  MCMC INITIAL=EM;
  VAR BASE DAY08 DAY15 DAY22 DAY43;
RUN;
```

The MI datasets will be used to calculate cure based on each respective secondary endpoint. The following SAS® code will then be used to calculate the difference of proportions for each imputed dataset and combine the analyses across imputations:

```
PROC SORT DATA=OUT1; BY _IMPUTATION_; RUN;
PROC FREQ DATA=OUT1;
  BY _IMPUTATION_ ;
  TABLES TRT*CURE / RISKDIFF CL;
  ODS OUTPUT RISKDIFFCOL2=PROP;
RUN;
PROC MIANALYZE DATA=PROP;
  WHERE ROW='Difference';
  MODELEFFECTS RISK;
  STDERR ASE;
  ODS OUTPUT PARAMETERESTIMATES=PEST;
RUN;
```

Comparisons will be one-sided using an α of 0.025.

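### Twenty imputations leave small but avoidable seed-to-seed noise in the confirmatory erythema-cure test; 100 or more would cut it at no statistical cost

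*SAP*

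**What the plan says.** SAP Section 13.2 generates the imputed data for the secondary endpoints with "PROC MI DATA=INDATA SEED=10719 NIMPUTE=20 OUT=OUT1 MINIMUM=0 MAXIMUM=4 ROUND=1". The primary analysis in Section 13.1 has the same setting with another seed, "PROC MI DATA=INDATA SEED=19107 NIMPUTE=20 OUT=OUT1 MINIMUM=0 MAXIMUM=4 ROUND=1". The vehicle-based analysis in Section 13.1.1.1 begins with "PROC MI DATA=INDATA SEED=43623 NIMPUTE=20 OUT=MDATA". Neither document gives a reason for 20 or a target for Monte Carlo error, and Protocol Section 9.4.2 names multiple imputation without a number.

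The pooled result is tested against a fixed threshold: "Comparisons will be one-sided using an α of 0.025". Under SAP Section 8.5, the largest of the three secondary p-values is compared with 0.025. If it passes, all three endpoints are declared significant. Otherwise the lower cut-offs are 0.0125 and 0.0083.

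On planned loss, Protocol Section 9.2 states: "Accounting for a 30% discontinuation, approximately 209 subjects per arm (approximately 418 total) will be randomized". SAP Section 5 describes an enrolment above the usual allowance, with extra "subjects due to concerns regarding the impact of COVID-19 and the possibility that up to two sites may be unable to complete the study".

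For erythema cure, SAP Section 5 assumes a "response rate of 19.1% for TP-03 and 7.4% for vehicle" and states: "For erythema cure, a sample size of 300 subjects will provide 88% power to demonstrate superiority of TP-03 to vehicle". The stated power for every other confirmatory endpoint is about 99% or more.

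**The concern.** Multiple imputation with a finite number of draws gives a p-value that depends partly on the random seed. The noise grows with the fraction of information that is missing and shrinks with the number of draws. It matters only when the p-value falls near a decision threshold.

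The primary endpoint has so much power that this hardly arises. Erythema cure has the least room. On the planning rates it is also the endpoint most likely to carry the largest secondary p-value, so its comparison with 0.025 decides both the erythema claim and the claim for all three secondary endpoints. If its p-value falls close to 0.025, the confirmatory conclusion could rest on which seed was written into the code.

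**Working it through.** **Inputs.** From SAP Section 5: erythema cure 19.1% vs 7.4%, and 88% power at 150 per arm. From SAP Section 13.2: one-sided alpha 0.025, 20 imputations. From Protocol Section 9.2: 209 randomized per arm to leave 150, which implies a loss of 1 − 150/209 = 28.2%. (An exact 30% would need 150/0.70 = 214.3, so 215 per arm; the gap is immaterial here.) Assumption: the multiply imputed share of Day 43 values is not given, so 5% to 28% is used, and the fraction of missing information λ is taken as equal to that share.

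**Step 1: the plan's own figure.** Pooled normal formula at 150 per arm:
- mean rate (0.191 + 0.074)/2 = 0.1325, so 1.96 × √(2 × 0.1325 × 0.8675) = 0.940
- √(0.191 × 0.809 + 0.074 × 0.926) = 0.472
- 0.117 × √150 = 1.433
- power = Φ((1.433 − 0.940)/0.472) = Φ(1.04) = 85.2%

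Exact and arcsine versions give 86.3% to 86.6%. The stated 88% is therefore reproduced only loosely, to within 2 points by those versions.

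**Step 2: noise near the cut-off.** Complete-data variance at 209 per arm is W = (0.154519 + 0.068524)/209 = 0.001067. With λ = 0.28, total variance is W/0.72 = 0.001482, so the SE is 0.0385. The Monte Carlo SE of the pooled difference, as a fraction of that SE, is √(λ/M): √(0.28/20) = 0.118 and √(0.28/100) = 0.053. Adding the noise in the estimated variance at z = 1.96:

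var(z) ≈ λ/M + 1.96² × λ² × 2/(M − 1)/4

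- M = 20: 0.0140 + 0.0079 = 0.0219, SD 0.148
- M = 100: 0.0028 + 0.0015 = 0.0043, SD 0.066

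A p-value centred at 0.025 then has a 95% seed range of z = 1.96 ± 0.290, or p from 0.012 to 0.047, with 20 draws. With 100 draws it is 1.96 ± 0.129, or p from 0.018 to 0.034. Averaged over all simulated trials the SDs are larger (0.19 and 0.08), but most of those trials lie well above the cut-off, so the values near 1.96 are the relevant ones.

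**Step 3: how often a trial is that close.** The expected z at λ = 0.28 is 0.117/0.0385 = 3.04, about one unit above 1.96. Most trials are safe from the seed.

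**Step 4: simulated disagreement.** Model: 209 per arm at the SAP's rates, Day 43 values missing at random within arm, beta-binomial imputation by arm, Rubin's rules, independent seeds applied to the same trial. Ranges are across three separate simulations; the top level was 28% in two and 30% in one.

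| Multiply imputed | Two seeds disagree, M = 20 | M = 100 |
|---|---|---|
| 5% | 0.5–0.7% | 0.2–0.3% |
| 10% | 1.1–1.4% | 0.4–0.6% |
| 20% | 2.5–2.7% | 1.0–1.2% |
| 28–30% | 3.8–4.3% | 1.6–1.7% |

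A single run can also be compared with the result from 2,000 imputations. The decision differs in 0.5%, 0.9%, 1.9% and 2.8% of trials at 5%, 10%, 20% and 28% with M = 20, and in 0.3%, 0.4%, 0.7% and 1.1% with M = 100. Power changes by less than one percentage point.

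**Step 5: one data set near the cut-off.** At 30% loss (209 × 0.70 = 146 observed per arm) with 22 vs 11 observed cures, 63% of seeds give significance with M = 20 and 85% with M = 100.

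**Step 6: closer to the SAP's model.** A small check (150 trials) used rounded normal-model imputation with the earlier visits, at assumed correlations of 0.3 to 0.6. At 30% loss, seeds disagreed in 4.9–6.7% of trials with M = 20 and 1.5–2.7% with M = 100. It is too small to refine Step 4, but it gives no sign that Step 4 overstates the effect.

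**The case against.** The strongest reply is that nothing here is wrong. Each seed is written into the SAP, so the result is reproducible and cannot be chosen afterwards. That stands. A reader might infer bias, an inflated type I error or scope for picking a seed; the documents support none of these.

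A reader might also take the 30% as the share of data that will be imputed. It is an enrolment allowance, raised for COVID-19 and possible site loss. Subjects who stop study drug are to stay in the study (Protocol Section 7.1), and withdrawals for lack of efficacy or adverse events are set to failure (SAP Section 2.6), which needs no seed. At 5% to 10% imputed, the gain from 100 draws is under one percentage point.

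It can fairly be added that 100 is itself a convention. At 30% imputed, two seeds still disagree in 1.7% of trials with 100 draws and in 0.7% with 500.

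Finally, SAP Section 13.2.1 plans a missing-as-failure analysis and observed-data analyses for erythema cure, all free of seeds. They would help to expose a fragile result. However, they rest on other missing-data assumptions and do not replace the confirmatory p-value.

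**Conclusion.** The point holds as a minor, optional improvement to the erythema-cure test in SAP Section 13.2. With 20 imputations, the chance that two valid seeds give opposite conclusions is about 0.7% to 4% over an assumed 5% to 28% multiply imputed, against about 0.2% to 1.7% with 100. The size rests on that assumed range, the Saturn-1 rates, 209 per arm and a simpler imputation model than the SAP's.

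It does not extend to the primary endpoint. At 44.0% vs 7.4%, computed power at 150 per arm exceeds 99.9%, so seed noise has no practical effect there. The other two secondary endpoints have stated power above 99%, so the lower Hochberg steps should seldom be decisive. What is exposed is the erythema claim and, through it, the claim for all three.

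**What to change.** In the PROC MI step of SAP Section 13.2, change NIMPUTE from 20 to 100 or more and keep seed 10719. Do this before unmasking.

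For consistency, the same change may be made in Section 13.1 and in the first PROC MI step of Section 13.1.1.1. The second step there draws once within each imputation and needs no edit.

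The estimand, imputation model, missing-data assumptions, seeds and alpha all stay as they are. The protocol gives no number of imputations, so nothing there conflicts. The cost is one number in one code block, or three if aligned, and a little computing time.

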13.2.1 SECONDARY EFFICACY ENDPOINTS

The first secondary efficacy endpoint is the proportion of subjects cured at Day 43, as defined by *Demodex* eradication (mite density of 0 mites/lash) in the analysis eye. Descriptive statistics will be presented by treatment arm.

Analysis will be conducted on the FAS, with intercurrent events handled as described in [Section 2.6](#). Discontinuation of study medication and non-optimal compliance will be ignored. Missing data due to withdrawal due to lack of efficacy or AEs will be imputed as failure. Missing data without withdrawal or withdrawal due to reasons other than lack of efficacy or AEs will be imputed employing MI using randomized treatment-based MCMC methodology as described in [Section 13.1](#). Testing of the percentage of subjects cured at Day 43 based on the *Demodex* eradication will be completed using a difference of proportions test.

In addition, a sensitivity analysis will be conducted in which all missing data will be imputed as failure. The difference of proportions test and Fisher's exact test will be used in this sensitivity analysis. Furthermore, the proportion of subjects cured based on *Demodex* eradication will be analyzed at all visits in both the analysis and fellow eye using observed data only. Stratified analyses will be conducted for the upper eyelid of the analysis eye by site, sex, age group, and race on the FAS using observed data only, unless p-values are not calculable due to sparsity or sample size limitations. In addition, if the COVID-19 Analysis Set consists of ≤95% of study subjects, the analysis will be conducted for the upper eyelid of the analysis eye at Day 43 on the COVID-19 Analysis Set with observed data only. These analyses will be conducted using similar SAS® code as described in [Section 13.1.1.3](#).

The second secondary efficacy endpoint is the proportion of subjects cured at Day 43, as defined by a composite score of 0 based on collarette and erythema scores in the analysis eye. Descriptive statistics will be presented by treatment arm.

Analysis will be conducted on the FAS, with intercurrent events handled as described in [Section 2.6](#). Discontinuation of study medication and non-optimal compliance will be ignored. Missing data due to withdrawal due to lack of efficacy or AEs will be imputed as failure. Missing data without withdrawal or withdrawal due to reasons other than lack of efficacy or AEs will be imputed employing MI using randomized treatment-based MCMC methodology as described in [Section 13.1](#). Testing of the percentage of subjects cured at Day 43 based on a composite score of 0 will be completed using a difference of proportions test.

In addition, a sensitivity analysis will be conducted in which all missing data will be imputed as failure. The difference of proportions test and Fisher's exact test will be used in this sensitivity analysis. Furthermore, the proportion of subjects cured based on a composite score of 0 for collarette and erythema scores will be analyzed at all visits in both the analysis and fellow eye, and both the upper and lower eyelid, using observed data only. Stratified analyses will be conducted for the upper eyelid of the analysis eye by site, sex, age group, and race on the FAS using observed data only, unless p-values are not calculable due to sparsity or sample size limitations. In addition, if the COVID-19 Analysis Set consists of ≤95% of study subjects, the analysis will be conducted for the upper eyelid of the analysis eye at Day 43 on the COVID-

19 Analysis Set with observed data only. These analyses will be conducted using similar SAS® code as described in [Section 13.1.1.3](#).

The third secondary efficacy endpoint is the proportion of subjects cured at Day 43, as defined by an erythema score of 0 in the analysis eye. Descriptive statistics will be presented by treatment arm.

Analysis will be conducted on the FAS, with intercurrent events handled as described in [Section 2.6](#). Discontinuation of study medication and non-optimal compliance will be ignored. Missing data due to withdrawal due to lack of efficacy or AEs will be imputed as failure. Missing data without withdrawal or withdrawal due to reasons other than lack of efficacy or AEs will be imputed employing MI using randomized treatment-based MCMC methodology as described in [Section 13.1](#). Testing of the percentage of subjects cured at Day 43 based on an erythema cure of 0 will be completed using a difference of proportions test.

In addition, a sensitivity analysis will be conducted in which all missing data will be imputed as failure. The difference of proportions test and Fisher's exact test will be used in this sensitivity analysis. Furthermore, the proportion of subjects based on an erythema cure of 0 will be analyzed at all visits in both the analysis and fellow eye, and both the upper and lower eyelid, using observed data only. Stratified analyses will be conducted for the upper eyelid of the analysis eye by site, sex, age group, and race on the FAS using observed data only, unless p-values are not calculable due to sparsity or sample size limitations. In addition, if the COVID-19 Analysis Set consists of $\leq 95\%$ of study subjects, the analysis will be conducted for the upper eyelid of the analysis eye at Day 43 on the COVID-19 Analysis Set with observed data only. These analyses will be conducted using similar SAS® code as described in [Section 13.1.1.3](#).

[REDACTED]

[REDACTED]

[REDACTED]

[REDACTED]

[REDACTED]

[REDACTED]

[REDACTED]

[REDACTED]

[REDACTED]

14. Safety Analyses

All safety analyses will be conducted using the Safety set. Safety analyses will be conducted for each milestone as described in [Section 2.7](#) and in the sections below.

14.1 Treatment Exposure

Duration of treatment exposure for completed or discontinued subjects will be calculated in days using the following:

$$\text{Duration of Exposure (days)} = (\text{Date of Last Dose} - \text{Date of First Dose}) + 1$$

Duration of treatment exposure for subjects who were lost to follow-up will be calculated in days using the following:

$$\text{Duration of Exposure (days)} = (\text{Date of Last Recorded Dose} - \text{Date of First Dose}) + 1$$

After the completion of Milestone 1, duration of treatment exposure for each subject exposed to study drug will be summarized with continuous descriptive statistics for each treatment arm using the Safety set. A subject listing of treatment exposure, study drug installation, study drug accountability, and study drug kit assignment and replacement will also be produced.

